### **6.3.2 Summary Statistics**

Data will be summarised by means of summary statistics. For continuous data the following summary statistics will be presented: number of observations, mean, standard deviation (SD), minimum, Q1, median, Q3 and maximum. 95% CI of the mean will also be presented for efficacy and safety data. Change from baseline to each post-baseline visit will be also described using descriptive statistics. Categorical data will be presented as counts and percentages.

Summary statistics will be presented by treatment group and visit, as applicable.

Certain presentations (withdrawals, patient exclusion from datasets, baseline and background characteristics and primary efficacy data) may be broken down by study center, if relevant.

All data collected during study follow-up will be displayed and analyzed according to the actual visit data in the eCRF.

### **6.3.3 Patient/Patient Data Listings**

Data collected in the eCRF will generally be listed. eCRF check questions and reminders will not be listed.

Listings will be sorted by study center, patient number, visit (where applicable) and time point (where applicable).

All derived data will be presented in the corresponding data listings.

### **6.3.4 Demographic and Other Baseline Characteristics**

Patient disposition, demographic data and other baseline data will be listed and presented using summary statistics.

Demographic data:

Age, gender, ethnicity, race, weight (pounds), height (inches) and BMI will be summarized by treatment regimen and overall. SAF, FAS and PP population will be used for this presentation.

#### **Relevant Medical History:**

Medical history data will be coded according to the Medical Dictionary for Regulatory Activities (MedDRA), the latest version. Medical history will be summarized for the SAF by treatment regimen and overall on a per-patient basis (e.g., if a patient reported the same event repeatedly the event will be counted only once at the specific level of display). Absolute counts (n) and percentages (%) will be presented for the number of patients with at least one Medical History event, and per System Organ Class (SOC) and per Preferred Term (PT) within SOC.

A listing will present all history-related data for the SAF.

#### **Other clinical baseline characteristics:**

Urine pregnancy test results and cataract diagnosis date and study eye will be listed for the SAF. Patient disposition will be presented, based on individual study examination dates and end of study status. A listing will be provided (if applicable) for discontinued patients.

### **6.3.5 Primary Efficacy analysis**

The primary efficacy endpoint in this clinical trial is the proportion of patients with anterior chamber cell grade of "0" (absence of cells) compared to placebo at Day 8.

The statistical hypothesis that will be tested for primary efficacy is described as:

- Null Hypothesis ( $H_0$ ): The difference in proportion of patients with anterior chamber cell grade of "0" at Day 8 between treatment regimes = 0.
- Alternative Hypothesis ( $H_1$ ): The difference in proportion of patients with anterior chamber cell grade of "0" at Day 8 between treatment regimes  $\neq 0$ .

The aim of the primary analysis of this study is to assess the superiority of clobetasol propionate ophthalmic nanoemulsion 0.05% compared to placebo with respect to the primary efficacy endpoint. The primary analysis will be based on a single study eye for each patient. Each patient's study eye will be defined as the surgery eye.

A Chi-Square test will be employed to test the proportion of study eyes with complete clearing of anterior chamber cells (count cell = 0) at Visit 3 (Day 8  $\pm$  1 day) without receiving rescue medication as compared between clobetasol propionate ophthalmic nanoemulsion 0.05% dosed QID and placebo dosed QID. The proportion of eyes with absence of cells (anterior chamber cell grade=0) together with its 95% confidence interval (CI) will be presented. Analysis will be conducted both in FAS and PP to test the robustness of the results.

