## 5. STUDY POPULATION

### 5.1 Inclusion Criteria

Patients will be eligible for study participation if they meet all of the following criteria:

- 1) Male or female, age 18 years or older on day of consent
- 2) Patients with routine unilateral cataract surgery on the day prior to study randomization
- 3) Patients with at least 5 cells in anterior chamber on the first day after surgery (at Visit 1)
- 4) Willing and able to understand and provide written ICF (at Visit -1)
- 5) Women who satisfy one of the following:
  - a) Are of child-bearing potential who are not pregnant or lactating and who are either abstinent or sexually active on an acceptable method of birth control (methods that can achieve a failure rate of less than 1% per year when used consistently and correctly, like hormonal contraception (oral pills, implantable device, or skin patch), intrauterine device, bilateral tubal occlusion, or double barrier) for at least 4 weeks prior to Visit 1 and throughout the study (i.e., until Day 29),  
OR
  - b) Are post-menopausal (have had no menstrual cycle for at least one year prior to Visit -1) or have undergone a sterilization procedure (bilateral tubal ligation, hysterectomy, hysterectomy with unilateral or bilateral oophorectomy or bilateral oophorectomy) at least 6 months prior to Visit -1

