#### 9.1.1 *Sample Size*

A two group  $\chi^2$  test with a 0.05 two-sided significance level will have 80% power to detect the difference between a proportion with complete resolution of anterior chamber cells in the active group of 0.22 and the placebo group proportion of 0.07 (odds ratio of 3.747) when the sample size is 202. Considering a 4% lost to follow-up rate a final sample size of 210 patients will be required (140 clobetasol, 70 placebo, in a 2:1 randomization ratio).

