### **9.1.10 Primary Analysis**

The aim of the primary analysis of this study is to assess the superiority of clobetasol propionate ophthalmic nanoemulsion 0.05% compared to placebo with respect to the primary endpoint in the FAS.

The primary analysis will be based on a single study eye for each patient. Each patient's study eye will be defined as the surgery eye.

The test will be the proportion of study eyes with complete clearing of anterior chamber cells (count cell = 0) at Visit 3 (Day 8 ± 1 day) without receiving rescue medication as compared between clobetasol propionate ophthalmic nanoemulsion 0.05% dosed QID and placebo dosed QID using the chi square statistic.

The PP population set will be also tested to confirm the robustness of the primary analysis.

The primary estimand (efficacy estimand) will be defined as the effect of the randomized treatments in all subjects meeting selection criteria assuming continuation of randomized treatments for the duration of the study regardless of actual compliance.

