### 6.5 Adjustment for Covariates

Baseline value will be used as a covariate in the MMRM analyses for the continuous secondary efficacy endpoints (see Section 6.3.6).

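### The primary Day 8 clearance test is valid and adequately powered, but leaves out the Visit 1 cell grade; stratifying by it is a cheap improvement worth roughly 0 to 3 points of power

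*SAP*

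**What the plan says.** - **Primary test.** SAP 6.3.5: "A Chi-Square test will be employed to test the proportion of study eyes with complete clearing of anterior chamber cells". Protocol 9.1.10 agrees, comparing active with "placebo dosed QID using the chi square statistic". SAP 6.3.5 sets the null hypothesis as a zero difference in proportions.
- **Covariates.** SAP 6.5: "Baseline value will be used as a covariate in the MMRM analyses for the continuous secondary efficacy endpoints". SAP 6.3.6.2 labels the secondary endpoints exploratory. SAP 6.7 rules out adjustment for center. The sensitivity analyses in SAP 6.3.7 concern intercurrent events only. No adjusted or stratified primary analysis appears, even as support.
- **Baseline cell grade.** Protocol 5.1 admits "Patients with at least 5 cells in anterior chamber on the first day after surgery" and sets no upper limit, so grades 0.5+ to 4+ can enter. Protocol 4.3.2.2 lists the slit-lamp cell assessment among the procedures before dosing, and protocol 9.1 makes Visit 1 the baseline.
- **Randomization.** Protocol 5.5 and 6.2.1 describe a blocked 2:1 schedule and state no stratification by cell grade.
- **Power.** Protocol 9.1.1 plans 80% power at a two-sided 0.05 level, for an "active group of 0.22 and the placebo group proportion of 0.07 (odds ratio of 3.747) when the sample size is 202". Allowing for 4% loss, it arrives at 210 patients, split as 140 on active and 70 on vehicle.

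**The concern.** Success on Day 8 means zero cells. An eye that starts at 5 cells plausibly has less to clear than one that starts at 40, so Visit 1 grade is a natural candidate predictor of the primary outcome. The plan adjusts for baseline in exploratory models and not in the test that decides the trial.

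Two things are at stake. If grade predicts clearance, a stratified test would have somewhat more power from the same patients. And with arms of 140 and 70 and no stated stratification, the arms may differ by chance in baseline inflammation. The plan has no pre-specified answer to that, and one devised after unmasking would carry little weight.

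**Working it through.** **1. The plan's own figure.** Inputs from protocol 9.1.1: p0 = 0.07, p1 = 0.22, 2:1 allocation, two-sided alpha 0.05, power 80%. The pooled rate is (0.07 + 2 × 0.22)/3 = 0.17. With pooled variance and no continuity correction:

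n(placebo) = [1.96 × √(0.17 × 0.83 × 1.5) + 0.8416 × √(0.07 × 0.93 + 0.22 × 0.78/2)]² / 0.15² = (0.902 + 0.327)² / 0.0225 ≈ 67.1

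The total is 3 × 67.09 = 201.3, against 202 stated. Power is 80.2% at N = 202 and 81.8% at N = 210. The odds ratio is (0.22/0.78)/(0.07/0.93) = 3.747, as stated. Exact enumeration at 70 v 140 gives power of 83.4%, and a type I error of 4.7% at a common rate of 0.07. The planned test therefore does what the protocol claims.

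**2. What stratifying would change.** The documents do not give the inputs this needs, so these are assumptions:
- the baseline mix over 0.5+/1+/2+/3+, with 4+ taken as empty;
- the factor by which the odds of clearance fall per grade;
- 4% missing counted as failure, so response rates of 0.96 × 0.22 = 21.1% and 0.96 × 0.07 = 6.7%.

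Each scenario has 20,000 simulated trials of 140 v 70. The CMH test uses three strata: 0.5+/1+, 2+ and 3+/4+. The Monte Carlo standard error of one power figure is about √(0.82 × 0.18/20,000) = 0.3 points.

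| Odds ratio per grade | Mix 10/45/35/10%: chi-square v CMH | Gain | Mix 25/40/25/10%: chi-square v CMH | Gain |
|---|---|---|---|---|
| 1 | 81.7 v 81.2% | -0.5 | 81.0 v 80.6% | -0.4 |
| 2 | 81.9 v 82.5% | +0.6 | 81.5 v 82.2% | +0.7 |
| 3 | 81.3 v 83.3% | +2.0 | 81.9 v 83.7% | +1.8 |
| 5 | 81.6 v 84.9% | +3.3 | 81.1 v 83.8% | +2.7 |

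With a more concentrated mix (10/70/17/3%), the gains are +0.2, +0.6 and +1.2 points at odds ratios of 2, 3 and 5. CMH type I error was 4.6 to 5.1%.

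**3. Number of strata.** Four separate grades give more under the strongest assumption. In another run with the 10/45/35/10% mix at an odds ratio of 5, power was 81.2% for chi-square, 84.4% for three strata and 86.8% for four. Merging 0.5+ with 1+ gives up part of the gain. The reason to merge is sparseness: about 70 × 0.07 = 4.9 placebo responders are expected.

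**4. Chance imbalance.** In about one trial in six, the active arm starts more than one standard deviation (of the between-arm difference) worse in mean grade. In those trials, for the first two mixes:

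| Odds ratio per grade | Chi-square v CMH, 10/45/35/10% | Chi-square v CMH, 25/40/25/10% |
|---|---|---|
| 2 | 74.7 v 82.4% | 73.1 v 80.5% |
| 3 | 70.5 v 82.1% | 71.2 v 82.6% |
| 5 | 66.3 v 82.5% | 65.1 v 80.8% |

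These trials are already counted in the averages of step 2. They are not a further loss.

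**The case against.** The strongest reply is that nothing here is broken. The sample size was computed for this same chi-square, the figure reproduces, and the hypothesis is a marginal difference in proportions, which the chi-square tests directly. All of that stands.

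A reader might go further than the documents allow in four ways.
- **That chance imbalance makes the test invalid.** It does not. The overall type I error of the unadjusted test already averages over random imbalances. Error rises only conditionally: with a common 15% response rate and the active arm starting that much worse, it was 5.4 to 7.8% for chi-square at odds ratios of 2 to 5, against 4.9 to 5.4% for CMH. That is an argument about robustness.
- **That Visit 1 grade is a strong predictor.** It is plausible, but the documents report no association. Entry at 5 cells also narrows the range: grade 0.5+ covers 1 to 5 cells, so it can hold only eligible eyes with exactly 5.
- **That 5 or 6 points of power are being lost.** Gains of that size need very strong prognosis and a finer analysis than the three strata proposed here.
- **That the change is free.** It needs no new data. It does need an amendment, and it loses a little power if grade is not prognostic.

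It is also fair to say that imbalance would be visible, since SAP Table 14.2.4.2 shows baseline grades by arm. But seeing an imbalance does not settle how the primary result should allow for it.

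**Conclusion.** The point holds as a cheap improvement. The plan does not use a pre-dose measurement of its own primary variable in the primary test, and has no supportive analysis that does. The test as planned is valid and meets its stated 80% power.

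For the three strata proposed, the change in average power is about -0.4 points if grade is not prognostic, 0 to +1 at an odds ratio of 2 per grade, 0 to +2 at 3 and +1 to +3 at 5, with type I error about 5%. These figures rest on assumed grade mixes and an assumed prognostic strength, and on missing outcomes counted as failures. The more useful benefit may be a pre-specified answer to an unlucky baseline imbalance: even at an odds ratio of 2, that situation takes the unadjusted test down to 73 to 75% power, against 80 to 82% for the stratified test, under the first two mixes.

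**What to change.** Before unmasking, by the amendment that protocol 9.2 requires for a change to the primary method:
- Make the primary test a CMH test stratified by Visit 1 cell grade in three strata (0.5+/1+, 2+, 3+/4+), in the same FAS and with the same responder rule.
- Report a CMH-weighted or standardized risk difference with its 95% confidence interval, so that the estimate matches the difference-in-proportions hypothesis in SAP 6.3.5. A logistic odds ratio would not: it is conditional on grade, and came out at about 3.8 to 4.8 in simulation against a marginal 3.75.
- State in advance how sparse strata will be handled. With about 5 placebo responders expected, the strata should not be made finer.
- Keep the unadjusted chi-square as a supportive analysis.

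The cost is one amendment, matching SAP text, and up to about half a point of power if grade is not prognostic. No extra patients, visits or data are needed. If the sponsor prefers to leave the primary test as it is, pre-specifying the stratified analysis as supportive in the SAP is the minimum.

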### **6.3.6 Secondary Efficacy Analyses**

#### **6.3.6.1 Key Secondary Efficacy Analysis**

The key secondary efficacy endpoint is the proportion of patients with VAS pain score of "0" (no eye pain) compared to placebo at Day 8.

The key secondary analysis will be based on a single study eye for each patient. Each patient's study eye will be defined as the surgery eye.

A Chi-Square test will be performed to test the proportion of study eyes with no pain (VAS = 0) at Visit 3 (Day 8 ± 1 day) without receiving rescue medication as compared between clobetasol propionate ophthalmic nanoemulsion 0.05% dosed QID and placebo dosed QID. The proportion of eyes with no pain together with its 95% confidence interval (CI) will be presented.

Analysis will be conducted both in FAS and PP to test the robustness of the results.

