**4.3.2.2 Visit 1 (Baseline visit at Day 1, 24 h after the cataract surgery)**

At Visit 1, the following activities and assessments will be performed (**NOTE:** All ocular assessments must be performed in both eyes):

Prior to IMP administration:

- Inclusion/exclusion criteria assessment
- Relevant medical history
- Urine pregnancy test – only for females of childbearing potential
- Eye pain (VAS) – to be assessed prior to any physical evaluation
- Eye discomfort – to be assessed prior to any physical evaluation
- Photophobia (VAS) – to be assessed prior to any physical evaluation
- Vital signs examination (temperature, blood pressure and pulse) – to be completed 15 min before any ocular assessment; also to be completed at least  $30 \pm 10$  min before IMP administration
- Slit-lamp examination
  - ✓ Anterior chamber cell
  - ✓ Anterior chamber flare
  - ✓ Chemosis
  - ✓ Bulbar conjunctival injection
  - ✓ Ciliary injection
  - ✓ Corneal edema
  - ✓ Keratic precipitates
- IOP
- BCVA measured by Snellen chart
- Indirect ophthalmoscopy
- Prior medications
- Randomization of the patient
- Dispensation of IMP and administration of the first dose

After IMP administration:

- Distribution of patient diary:
  - Throughout the study, patients or caregivers should record on it: doses and schedule of IMP administration, eye pain VAS scores and cataract surgery-associated symptoms.
- Concomitant medications
- AE assessment (**NOTE:** Expected changes or the presence of inflammation or pain resulting from routine cataract surgery will not be captured as AEs. Additionally, the routine cataract surgery at Day –1 will not be reported as an AE.)

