## 9. STATISTICAL METHODS

### 9.1 General Statistical Methods

In general, data will be summarized by means of summary statistics. Continuous data will be presented with the number of observations, mean value, confidence intervals, standard deviation, minimum, Q1, median, Q3 and maximum value. Change from baseline to each post-baseline visit will be also described using descriptive statistics. Categorical data will be presented as counts and percentages.

The data will be presented for each treatment group by visit.

Individual patient data will be listed for all enrolled patients. Listings will be sorted by center and patient number and labelled by randomized treatment group.

Before unmasking the study data, a separate statistical analysis plan (SAP), which will provide the technical details of the statistical analysis outlined below, will be prepared and approved.

For statistical analyses, the following definitions will be applied:

- Baseline: Baseline is defined as Visit 1 (Day 1, 24 h after the cataract surgery).
- Randomized treatment group: The treatment that was assigned at the time of randomization.

The assessments performed at Visit 1 (Day 1) will be considered the baseline values.

All data collected during study follow-up will be displayed and analyzed according to the actual visit data in the eCRF.

Unless otherwise stated, all statistical tests will be conducted using two-sided alpha = 0.05.

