### **9.1.11 Key Secondary Analysis**

The aim of the key secondary analysis of this study is to assess the superiority of clobetasol propionate ophthalmic nanoemulsion 0.05% compared to placebo with respect to the key secondary endpoint in the FAS.

The key secondary analysis will be based on a single study eye for each patient. Each patient's study eye will be defined as the surgery eye.

The test will be the proportion of study eyes with no pain (pain = 0) at Visit 3 (Day 8 ± 1 day) without receiving rescue medication as compared between clobetasol propionate ophthalmic nanoemulsion 0.05% dosed QID and placebo dosed QID using the chi square statistic.

The PP population set will be also tested to confirm the robustness of the key secondary analysis.

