Between treatment comparison of the evolution over time will be analysed using a Restricted Maximum Likelihood (REML)-based repeated measures approach (Mixed Model Repeated Measures [MMRM]). The model for analysis will include the change from baseline as a dependent variable, the baseline score as a covariate, the categorical fixed effects of treatment (IMP, Placebo) and visit and the interaction treatment\*visit. An unstructured (co)variance structure will be used to model the within-patient errors. If this analysis fails to converge, alternative covariance structures will be tested. Akaike's information criterion will be used to determine the best fit (smaller AIC).

If it is not possible to apply a MMRM due to the non-normality of the variable, the Mann Whitney Wilcoxon test will be performed.

Secondary efficacy analyses will be performed on the FAS population.

The PP population set will be also tested to confirm the robustness of the secondary analyses.

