14.2.10.4	Change from Baseline to Day 3, Day 8, Day 15 and Day 29 compared to placebo in the proportion of patients with corneal edema (yes/no)	FAS	
14.2.10.5	Change from Baseline to Day 3, Day 8, Day 15 and Day 29 compared to placebo in the proportion of patients with keratic precipitates (yes/no)	FAS	
14.2.11.1	Change from Baseline to Day 3, Day 8, Day 15 and Day 29 compared to placebo in the severity of chemosis. Improvement or no Improvement.	FAS	
14.2.11.2	Change from Baseline to Day 3, Day 8, Day 15 and Day 29 compared to placebo in the severity of chemosis. Descriptive table	FAS	
14.2.11.3	Change from Baseline to Day 3, Day 8, Day 15 and Day 29 compared to placebo in the severity of bulbar conjunctival injection. Improvement or no Improvement.	FAS	
14.2.11.4	Change from Baseline to Day 3, Day 8, Day 15 and Day 29 compared to placebo in the severity of bulbar conjunctival injection. Descriptive table	FAS	
14.2.11.5	Change from Baseline to Day 3, Day 8, Day 15 and Day 29 compared to placebo in the severity of ciliary injection. Improvement or no Improvement	FAS	
14.2.11.6	Change from Baseline to Day 3, Day 8, Day 15 and Day 29 compared to placebo in the severity of ciliary injection. Descriptive table	FAS	
14.2.11.7	Change from Baseline to Day 3, Day 8, Day 15 and Day 29 compared to placebo in the severity of corneal edema. Improvement or no Improvement.	FAS	

14.2.11.8	Change from Baseline to Day 3, Day 8, Day 15 and Day 29 compared to placebo in the severity of corneal edema. Descriptive table	FAS	
14.2.11.9	Change from Baseline to Day 3, Day 8, Day 15 and Day 29 compared to placebo in the severity of keratic precipitates. Improvement or no Improvement	FAS	
14.2.11.10	Change from Baseline to Day 3, Day 8, Day 15 and Day 29 compared to placebo in the severity of keratic precipitates. Descriptive table	FAS	
14.2.12	MMRM. Change from Baseline to Day 3, Day 8, Day 15 and Day 29 compared to placebo in the visual analog scale (VAS) photophobia score.	FAS	
14.2.13	MMRM. Change from Baseline to Day 8, Day 15 and Day 29 compared to placebo in Snellen best.corrected visual acuity (BCVA) score.	FAS	
14.2.14	MMRM. Change from Baseline to Day 3, Day 8, Day 15 and Day 29 compared to placebo in the VAS pain score.	FAS	X
14.2.15	Proportion of patients with VAS pain of "0" compared to placebo at Day 3, Day 15 and Day 29.	FAS	X

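### The Day 8 pain test leaves out baseline pain (valid, with an uncertain gain from adjusting), and no confidence interval for the treatment difference is planned for the primary endpoint

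*SAP*

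**What the plan says.** **Baseline pain is available.** Among the Visit 1 procedures that precede the first dose, Protocol 4.3.2.2 lists "Eye pain (VAS) – to be assessed prior to any physical evaluation". Protocol 9.1 adds: "The assessments performed at Visit 1 (Day 1) will be considered the baseline values".

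**The key secondary test does not use it.** Protocol 9.1.11 says: "The test will be the proportion of study eyes with no pain (pain = 0) at Visit 3". It uses a chi-square statistic and counts only eyes that had no rescue medication. SAP 6.3.6.1 repeats this: "A Chi-Square test will be performed to test the proportion of study eyes with no pain (VAS = 0) at Visit 3".

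**The exploratory pain model does use it.** SAP 6.5 says: "Baseline value will be used as a covariate in the MMRM analyses for the continuous secondary efficacy endpoints". SAP 6.3.6.2 specifies: "The model for analysis will include the change from baseline as a dependent variable, the baseline score as a covariate". Table 14.2.14 applies that model to VAS pain, including Day 8: "MMRM. Change from Baseline to Day 3, Day 8, Day 15 and Day 29 compared to placebo in the VAS pain score".

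**Intervals.** SAP 6.3.5 writes the primary null and alternative hypotheses as a difference, each beginning "The difference in proportion of patients with anterior chamber cell grade of" and going on to grade 0 at Day 8. The interval it then plans is for the proportion. SAP 6.3.6.1 does the same for pain. Protocol 9.1.10 and 9.1.11 mention no interval. Protocol 9.1.12 and the synopsis do plan intervals on the difference from placebo for categorical secondary variables. The matching text in SAP 6.3.6.2 gives an interval only for each category percentage.

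**The concern.** Entry requires anterior chamber cells but not pain (Protocol 5.1), so a patient can be randomized at VAS 0, which is already the response value. Baseline pain is therefore a natural candidate predictor of Day 8 pain, and it will be in the database at no extra cost. The sample size covers only the primary endpoint. No power is stated for the key secondary, so a cheap gain would be welcome if there is one.

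For the primary endpoint, the plan tests a difference without committing to estimate it with its uncertainty. Readers would then compare two separate arm intervals. Such intervals often overlap when the test is significant, so a positive result can look inconclusive.

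**Working it through.** **1. The plan's own figure.** Inputs (Protocol 9.1.1, SAP 4.2): 0.22 vs 0.07, two-sided 0.05, 80% power, 2:1 allocation. The pooled rate is (2 × 0.22 + 0.07)/3 = 0.17.

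n(placebo) = [1.96√(1.5 × 0.17 × 0.83) + 0.8416√(0.07 × 0.93 + 0.22 × 0.78/2)]² / 0.15² = (0.902 + 0.327)² / 0.0225 ≈ 67.1

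The total is 3 × 67.1 ≈ 201.3, which agrees with 202 (204 if each arm is rounded up). Power at 202 is 80.2%. This says nothing about pain: the documents give no Day 8 pain-free rates, no share starting at VAS 0 and no prognostic strength for baseline pain.

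**2. What adjustment could change.** All inputs except 140/70 and alpha are assumptions:
- Pain-free rates, placebo/active: 0.40/0.60, 0.55/0.74 and 0.70/0.86, chosen to give crude power of 78 to 79%.
- Share at baseline VAS 0: 30, 55 or 87%. The last two borrow from the background survey in Protocol 2.1 (55% without pain or discomfort; 55 + 32 = 87% with slight discomfort added). That survey has no time point and is not this population.
- Prognostic odds ratio (OR) for being pain-free at Day 8, baseline VAS 0 vs above 0: 1, 2, 3 or 6.

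The comparator is the Cochran-Mantel-Haenszel (CMH) test over the two baseline strata k:

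[Σ(aₖ − n₁ₖmₖ/Nₖ)]² / Σ[n₁ₖn₀ₖmₖ(Nₖ − mₖ)/(Nₖ²(Nₖ − 1))]

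Here a is active responders, m all responders, n₁ and n₀ the arm sizes, and N the stratum size. There were 200,000 simulated trials per cell. For the common-odds-ratio cells the standard error of each power difference is 0.03 to 0.07 points.

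CMH power minus chi-square power, in points:

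| Prognostic OR | Common treatment odds ratio | Effect only in patients with baseline pain |
|---|---|---|
| 1 | -0.5 to 0.0 | +0.8 to +2.6 |
| 2 | -0.1 to +1.2 | -0.3 to +0.2 |
| 3 | +0.5 to +2.8 | -0.6 to +0.6 |
| 6 | +1.8 to +6.9 | +0.6 to +2.6 |

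Repeat runs put the outer limits at about -0.6 and +7.0 (common odds ratio) and about -0.5 and +2.6 (confined effect).

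The last column uses shares of 30 and 55% only. At 87% the pain stratum would need a rise of 0.16/0.13 = 1.23 or more, which is impossible. An effect confined to VAS 0 patients gives larger gains than a common odds ratio, so these ranges are not bounds.

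Under the null, with rates of 0.40, 0.55 and 0.70, the chi-square rejects in 5.0 to 5.2% of trials and CMH in 4.9 to 5.1%. Both are valid.

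A cross-check with logistic adjustment for a continuous baseline gave about -1 to +12 points, again depending on the assumed prognostic strength.

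**3. The missing interval.** Take 31/140 vs 5/70, about the primary design rates. The Wilson arm intervals are 16.1 to 29.7% and 3.1 to 15.7%. The difference is 0.2214 − 0.0714 = 0.150. Newcombe limits:
- Lower: 0.150 − √[(0.2214 − 0.1606)² + (0.1566 − 0.0714)²] = 0.045
- Upper: 0.150 + √[(0.2971 − 0.2214)² + (0.0714 − 0.0309)²] = 0.236

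Exact enumeration at 0.22 vs 0.07 with 140/70 gives power of 83.4%. Among significant results the arm intervals overlap in 18% (Wald), 35% (Wilson) or 41% (Clopper-Pearson) of trials. The SAP names no method. The Newcombe interval covers in 95.6% and disagrees with the chi-square in 0.6%.

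**The case against.** The unadjusted chi-square is pre-specified, the two documents agree on it, and it holds its error rate. Randomization is described as blocked, with no pain stratum that the analysis would have to reflect. Every power gain above rests on assumed inputs, and the larger ones also need a common odds ratio. That is doubtful here, because a patient at VAS 0 has no pain to clear. With the effect confined to patients who have pain, CMH can lose about half a point even when baseline pain is prognostic. It also needs a cut-point and a missing-baseline rule, and the Mantel-Haenszel interval and the CMH test disagree on significance in 0.5 to 3.5% of trials. All of this stands.

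A reader might infer that the chi-square is wrong or clearly underpowered. The documents do not support that. Nor do they show that 55% of these patients start pain-free.

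A reader might also infer that separate arm intervals are the only ones planned. That is true of the primary, but not of everything. Protocol 9.1.12 plans difference intervals for categorical secondary variables, and both documents file the key secondary under secondary. The SAP exists to supply technical detail, so its silence does not cancel the protocol. Protocol 9.1.12 also plans an adjusted difference with an interval for continuous endpoints, which takes in VAS pain change at Day 8, a different and exploratory endpoint.

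Finally, the difference interval follows from the two-by-two counts, and a reader who looks at the p-value will not be misled by overlap. That limits the weight of the gap but does not close it.

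**Conclusion.** The point holds in a limited form.

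**Baseline pain.** The key secondary test is valid but ignores a baseline measurement that the plan already collects and uses elsewhere. The effect on power is uncertain: about -0.6 to +7 points under a common odds ratio and about -0.5 to +2.6 points if only patients with baseline pain benefit. Both ranges assume 140/70, crude power of 78 to 79% and a prognostic odds ratio of 1 to 6. The gain may be nil. Pre-specifying the adjusted analysis is worthwhile because it is cheap and the likely loss is small, not because a gain is assured.

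**Difference intervals.** On the primary, no document plans an interval for the quantity in the hypothesis. On the key secondary, the protocol can be read to plan one and the SAP does not carry it over. This is a minor estimation and reporting correction. It alters no test, error rate or population.

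**What to change.** Before unmasking, by the route in Protocol 9.2, revise the SAP and align Protocol 9.1.11:

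1. Pre-specify a baseline-pain-adjusted analysis of the key secondary, for example CMH by baseline VAS 0 vs above 0, with the Mantel-Haenszel risk difference and its 95% interval. Fix the strata and a rule for missing baseline VAS in advance. Report the crude chi-square beside it and state which of the two is the test of record.
2. Leave the primary chi-square unchanged. Add the unadjusted difference in proportions with a 95% interval, for example Newcombe. Carry the Protocol 9.1.12 difference intervals into the SAP for the categorical secondary variables, and say whether they include the key secondary. Any analysis of the primary stratified by baseline cell grade should be supportive only, since about 70 × 0.07 ≈ 5 placebo responders are expected.

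**Cost.** A SAP revision, an aligned protocol section and little programming; no new data. If the adjusted test becomes the test of record, up to about 0.6 points of power may be lost, and its interval may occasionally contradict it. If 87% start at VAS 0, the other stratum holds only 0.13 × 140 ≈ 18 active and 0.13 × 70 ≈ 9 placebo patients. The primary difference interval costs no power.
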